9.6. Monitoring pregnancies for potential Serious Adverse Events

There is no requirement to monitor pregnancies for potential Serious Adverse Events.

9.7. Reporting to the Competent Authority and Research Ethics Committee

9.7.1. Suspected Unexpected Serious Adverse Reactions

On becoming aware of a SUSAR, the Trial Manager (or delegate) will notify the Sponsor as soon as possible. The Sponsor will report a minimal data set of all individual events categorised as a fatal or life threatening SUSAR to the MHRA and Research Ethics Committee (REC) within 7 days. Detailed follow-up information will be provided within an additional 8 days. All other events categorised as SUSARs will be reported within 15 days.

SUSARs will be unblinded to allow reporting to REC and the MHRA.

Trial name:	Premature Ovarian Insufficiency Study of Effectiveness of hormonal therapy	Protocol version:	4.0	date:	01 Oct 2024	Page:	38
-------------	--	-------------------	-----	-------	-------------	-------	----

9.7.2. Serious Adverse Reactions

The NCTU will report details of all SAEs and SARs (including SUSARs) to the MHRA and REC annually from the date of the Clinical Trial Authorisation, in the form of a Development Safety Update Report (DSUR).

9.7.3. Adverse Events

Details of all AEs will be reported to the MHRA on request.

9.7.4. Other safety issues identified during the course of the trial

If any urgent safety measures are taken the CI shall immediately and, in any event, no later than 3 days from the date the measures are taken, give written notice to the MHRA, the relevant REC and the sponsor, of the measures taken and the circumstances giving rise to those measures

9.8. Investigators

Details of all SUSARs and any other safety issue which arises during the course of the trial will be reported to Principal Investigators. A copy of any such correspondence should be filed in the Investigator Site File.

9.9. Data Monitoring Committee

The independent DMC will review all SAEs.

9.10. Reporting to third parties

No reporting of adverse events to third parties is expected. Any safety issues identified during the course of the trial will be notified to the MHRA.

10. Data Handling and Record Keeping

10.1. Source Data

Source data is defined as all information in original records and certified copies of original records of clinical findings, observations, or other activities in a clinical trial necessary for the reconstruction and evaluation of the trial.

In order to allow for the accurate reconstruction of the trial and clinical management of the participant, source data will be accessible and maintained.

Source data is kept as part of the participant’s medical notes generated and maintained at site. Each site will record the location of source data at their site using a source data location log prior to commencing recruitment. Data that are not routinely collected elsewhere may be entered directly onto the eCRF; in such instances the eCRF will act as source data and this will be clearly defined in the source data location log and recorded. Some recruiting centres may initially record trial information into a source data worksheet; where this has been used this will be noted.

For this trial, source data refers to, though is not limited to, the participants’ medical notes, laboratory blood results, data recorded directly into the CRF, source data worksheets and questionnaires. (Questionnaires completed by participants on paper will be considered source data, if questionnaires are completed online by the participant the data in the eCRF will be considered source data).

Where paper follow-up questionnaires are issued to participants these will be entered into the eCRF by a member of the research team at site for data entry and will be considered source data. Where

Trial name:	Premature Ovarian Insufficiency Study of Effectiveness of hormonal therapy	Protocol version:	4.0	date:	01 Oct 2024	Page:	39
-------------	--	-------------------	-----	-------	-------------	-------	----

follow-up is obtained via telephone, this data will be entered directly into the eCRF or collected on paper proforma (where direct eCRF entry is not possible) by a member of the NCTU and will be considered source data.

10.2. Routine data

At 5 years follow-up, key outcomes e.g. cancer, bone fractures and cardiovascular events will be collected from NHS England routine data (or equivalents in devolved nations) using validated diagnostic codes and hospital episode data.

10.3. Electronic Case Report Form (eCRF) Completion

Data will be reported using an eCRF. Reported data will be consistent with the source data and any discrepancies will be explained. Staff delegated to complete the eCRF will be trained to adhere to ICH-GCP guidelines and trial specific guidance on the completion of the eCRF.

For instances where data may not be directly entered onto the eCRF, a set of trial specific data collection worksheets will be provided to the sites to facilitate collection of trial data prior to the site entering the data onto the eCRF.

In all cases it remains the responsibility of the site’s Principal Investigator to ensure that the eCRF has been completed correctly and that the data are accurate as evidenced by the signature of the site’s Principal Investigator on the eCRF.

10.4. Data Management

Details about data handling will be specified in the Data Management Plan (DMP). This will include the agreed validation specification which will validate data for consistency and integrity as it is entered.

All trial data will be entered onto a trial specific database through the eCRF with participants identified only by their unique trial number and initials. The database will be developed and maintained by NCTU. Access to the database will be restricted and secure. Any missing or ambiguous data will be queried with the site via the eCRF, sites should respond to the data queries in a timely manner, ideally within 2 weeks of the query being raised. All access and data transactions will be logged in a full audit trail.

Participant’s eCRF data will be reviewed and frozen on an ongoing basis once they are deemed to have a complete set of data that has passed data validation checks (i.e. there are no data queries outstanding). Once all participant data have been frozen and the statistical analysis plan has been finalised, the trial database will be locked (set to read only). This will be done prior to the data analysis. It is planned that there will be 2 database locks after 2 and 5 years follow up.

10.5. Archiving

It is the responsibility of the Principal Investigator to ensure all essential trial documentation and source documents (e.g. signed ICFs, ISFs, copies of CRFs etc.) at their site are securely retained for at least 25 years after the end of the trial. Documents will be archived following regulatory requirements and any local procedures. No documents will be destroyed without prior approval from the Sponsor.

10.6. Data sharing

Individual participant medical information obtained as a result of this trial is considered confidential and disclosure to third parties is prohibited with the exceptions noted in this protocol.

Trial name:	Premature Ovarian Insufficiency Study of Effectiveness of hormonal therapy	Protocol version:	4.0	date:	01 Oct 2024	Page:	40
-------------	--	-------------------	-----	-------	-------------	-------	----

Participants’ contact details, including name, address, telephone/mobile number and email will be shared between participating sites and NCTU for the purposes of issuing questionnaires and electronic reminders (text/email) for the trial.

Minimal linked anonymised data (participation identification code, initials and date of birth), used for labelling of laboratory samples (bone metabolism markers), will also be shared with the analysing laboratory.

Any personal data will be held in a secure database using encryption, with restricted password protected access. Only appropriate members of the participating site team and NCTU research team will have access to these data.

Participant confidentiality will be further ensured by utilising identification code numbers to correspond to treatment data in computer files.

Data generated as a result of this trial will be available for inspection on request by University College London, NCTU, the REC, local R&D departments and the regulatory authorities.

Anonymised participant data may be shared with researchers external to the trial research team in accordance with the NCTU’s data sharing procedure. All requests for data should be sent to the NCTU.

11. Quality control and quality assurance

11.1. Site Set-up and Initiation

All participating Principal Investigators will be asked to sign the necessary agreements and supply a current signed CV to the NCTU. All members of the site research team will also be required to sign a **site delegation log and training log**. Prior to commencing recruitment all sites will undergo a process of initiation and will have completed Good Clinical Practice (GCP) training (PIs will be required to evidence this with GCP certification). Key members of the site research team will be required to attend either a meeting or a teleconference covering aspects of the trial design, protocol procedures, Adverse Event reporting, collection and reporting of data and record keeping. Sites will be provided with an ISF containing essential documentation, instructions, and other documentation required for the conduct of the trial. The NCTU must be informed immediately of any change in the site research team.

11.2. Monitoring

Monitoring will be carried out as required following a risk assessment and as documented in the trial monitoring plan. The NCTU will be in regular contact with the site research team to check on progress and address any queries that they may have. The trial team will check incoming eCRF data for adherence with the protocol, data consistency, missing data and timing. Sites will be asked for missing data or clarification of inconsistencies or discrepancies. Additional monitoring (including on-site visits) may be triggered, for example by poor CRF return, poor data quality, lower/higher than expected SAE reporting rates, excessive number of participant withdrawals or deviations. If an on-site monitoring visit is required, NCTU will contact the site to arrange a date for the proposed visit and will provide the site with written confirmation. Investigators will allow NCTU trial/monitoring staff access to source documents as requested.

Sites will be requested to provide copies of signed ICFs and other documentation for in-house review for central monitoring for all participants. This will be detailed in the monitoring plan.

Trial name:	Premature Ovarian Insufficiency Study of Effectiveness of hormonal therapy	Protocol version:	4.0	date:	01 Oct 2024	Page:	41
-------------	--	-------------------	-----	-------	-------------	-------	----

11.3. Audit and Inspection

The Principal Investigator will permit trial-related monitoring, quality checks, audits, ethical reviews, and regulatory inspection(s) at their site, providing direct access to source data/documents. The Principal Investigator will comply with these visits and any required follow up. Sites are also requested to notify NCTU of any MHRA inspections.

The Trial Master File and evidence of audits will be made available upon request for regulatory inspections.

11.4. Notification of Serious Breaches

In accordance with Regulation 29A of the Medicines for Human Use (Clinical Trials) Regulations 2004 (and its amendments) the Sponsor of the trial is responsible for notifying the licensing authority in writing of any serious breach of the conditions and principles of GCP in connection with that trial or the protocol relating to that trial, within 7 days of becoming aware of that breach.

For the purposes of this regulation, a “serious breach” is a breach which is likely to affect to a significant degree the safety or physical or mental integrity of the subjects of the trial; or the scientific value of the trial. Sites are therefore requested to notify NCTU of any suspected trial-related serious breach of GCP and/or the trial protocol. Where NCTU is investigating whether or not a serious breach has occurred, sites are also requested to cooperate with NCTU in providing sufficient information to report the breach to the MHRA where required and in undertaking any corrective and/or preventive action.

Sites may be suspended from further recruitment in the event of serious and persistent non-adherence with the protocol and/or GCP, and/or poor recruitment. Any major problems identified during monitoring may be reported to the trial oversight committees (TMG, TSC, DMC), the REC and the relevant regulatory bodies. This includes reporting serious breaches of GCP and/or the trial protocol to the REC and MHRA.

12. End of Trial Definition

The end of trial will be **the date of final database lock**. NCTU will notify the MHRA and REC that the trial has ended within 90 days of the end of trial.

Where the trial has terminated early, NCTU will inform the MHRA and REC within 15 days of the end of trial. NCTU will provide them with a summary of the clinical trial report within 12 months of the end of trial.

13. Statistical Considerations

13.1.1. Power Calculations / sample size calculation

The original sample size was powered to detect a mean difference in lumbar spine BMD (g/cm²) of 0.05 between the HRT and the COC group at 2 years post-randomisation to ensure that the trial preserves at least the effect observed in a similar previous study¹⁷. This target difference also represented an absolute change thought to be the least significant change in spine BMD that is unlikely to be due to the precision error of the test. The precision error is best described using the smallest detectable difference, rather than the coefficient of variation, and for lumbar spine a change of BMD of at least +/-0.05g/cm² is considered clinically significant^{39,40}. Assuming that the lumbar spine BMD in each group varies with a standard deviation (SD) of 0.15, observed from 112 comparable patients in an unpublished cohort of POI women and the previous trial¹⁷, a total of 382 patients (191 per group)

Trial name:	Premature Ovarian Insufficiency Study of Effectiveness of hormonal therapy	Protocol version:	4.0	date:	01 Oct 2024	Page:	42
-------------	--	-------------------	-----	-------	-------------	-------	----

were required to detect the between-group difference of 0.05 g/cm² (a small effect size of 0.333) with a 90% power, 5% 2-sided significance level and 1:1 allocation. Attrition had been a major problem in studies of similar population, so we allowed for up to 20% loss to follow-up, requiring 480 patients to be recruited.

This sample size was expected to still have >80% power to detect a medium effect size (between-group mean difference of 0.075 g/cm², SD=0.15) between each HRT route (oral or transdermal) and the COC, assuming the proportion in one route is between 20% to 50%.

The above sample size was calculated without accounting for correlation between repeated outcome measures. At the design stage, it was decided not to account for the repeated measures design in the sample size calculation to be conservative as it was assumed that the efficiency gained by repeated measures would be offset by possible efficiency loss attributable to misspecification of any of the sample size parameters due to uncertainty about the assumptions.

At a review after 18 months of recruitment it was recommended by the Trial Steering Committee (TSC) that the sample size should be readjusted to account for the correlation between repeated outcome measures. No outcome data was available to the TSC or investigators when the decision was made. The revised sample size uses the same parameters as the original sample size calculation but are based on a mixed-effect model analysis of repeated measures data including a baseline and two repeated post-randomisation outcome measurements, with contrasts to assess treatment effects at each time point. The calculation assumes a compound symmetry covariance structure (exchangeable), with a common variance (σ^2) for the outcome measure and a common correlation (ρ) between repeated follow-up assessments (autocorrelation). For each value of σ^2 , the required sample size increases with the correlation ρ between follow-up measures such that a correlation of 1 gives a sample size equivalent to two-sample t-test. A value of $\rho=0.4$ to 0.6 is typical in many studies. At the time of the review, there was insufficient accrued data to calculate the autocorrelation, so a conservative autocorrelation between follow-up measures of 0.6 was chosen. The sample size required for analysis to estimate the same effect as the original calculation, with 90% power, is 304. Allowing for 20% loss to follow-up requires the recruitment of 380 participants. To achieve 80% power and allowing for 20% loss of primary outcome data, 286 participants would be required.

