3.1. Trial Design

Multi-centre prospective, open, two-group parallel randomised controlled, superiority trial with equal allocation (1:1) to receive either HRT or the COC. Recruitment of 380 women is required to achieve ≥ 90% power to detect a difference in mean of 0.05 g/cm² in lumbar spine BMD between HRT and the COC. Further information on sample size and randomisation can be found in Section 6 and Section 13.

Participants will start treatment according to their randomised treatment allocation. Long-term systemic hormone treatment is recommended at least until the age of natural menopause. For the purpose of this trial, participants will be advised to remain on their allocated treatment for a minimum duration of 2 years, however it is acknowledged that a number of factors may influence a participant’s choice of therapy over this time.

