13.3. Analysis of Outcome Measures

The analysis and reporting of the trial will be in accordance with CONSORT guidelines. A full statistical analysis plan (SAP) will be developed and agreed prior to database lock for the analysis of the primary outcome at 2 years.

Trial name:	Premature Ovarian Insufficiency Study of Effectiveness of hormonal therapy	Protocol version:	4.0	date:	01 Oct 2024	Page:	43
-------------	--	-------------------	-----	-------	-------------	-------	----

Appropriate descriptive statistics (mean, standard deviation, median, lower and upper quartiles, minimum, maximum or frequencies and percentages) for the demographic and clinical outcome measures at baseline will be used to assess balance between the randomised arms at baseline, but no formal statistical comparisons will be performed. Baseline characteristics will also be descriptively compared between those randomised and those analysed to see if the attrition has introduced any imbalances. Descriptive statistics appropriate for the outcome will also be presented for all outcomes at all collected time points by treatment group.

The primary comparative analysis will be based on intention-to-treat, analysing participants in the groups to which they were randomised. The evaluation of the primary outcome of BMD in the lumbar spine at 2 years will be performed using a mixed effects model to allow for all available follow-up data (1 year, 2 year) to be used, adjusted for the baseline BMD in the lumbar spine and the minimisation variables as fixed effects except site which will be entered as a random effect. The model will include a treatment by time interaction to obtain the estimates of treatment effect at each follow-up time, with 2 years being the primary evaluation. An interaction between each covariate and time will be added to get a different adjustment for each covariate at each time point. The estimated between group effect will be presented using the difference in means, with a 95% confidence interval. The primary treatment comparison will be the contrast between allocated treatment groups at 2 years.

Sensitivity analyses for the primary outcome will include:

- Complete case analysis based on observed outcome data at 2 years
- Use of multiple imputation with auxiliary variables (if applicable) not included in the primary analysis also included in the imputation model.

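### The revised sample sizes (304/380 at 90% power, 286 at 80%) come from a calculation that is not the planned primary contrast, with a generic correlation of 0.6 that is not conservative in that calculation

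*Protocol*

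**What the plan says.** Protocol section 13.1.1 first gives the original calculation. It needed "a total of 382 patients (191 per group") to detect the "between-group difference of 0.05 g/cm² (a small effect size of 0.333) with a 90% power, 5% 2-sided significance level and 1:1 allocation". The variability input is stated as: "Assuming that the lumbar spine BMD in each group varies with a standard deviation (SD) of 0.15". The same section justifies the target difference partly by measurement precision, describing 0.05 g/cm² as "the least significant change in spine BMD that is unlikely to be due to the precision error of the test" and naming the smallest detectable difference as the measure intended.

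The revision follows. "The revised sample size uses the same parameters as the original sample size calculation", now with repeated measures under compound symmetry. The text mentions a baseline and two follow-up measurements, with contrasts at each time point. It adds that the required size grows with the correlation between follow-up measures and equals the t-test size at a correlation of 1. It calls 0.4 to 0.6 typical across studies and says too few data had accrued to estimate the value, "so a conservative autocorrelation between follow-up measures of 0.6 was chosen". The results are 304 analysed and 380 recruited for 90% power, and 286 recruited for 80%.

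Section 3.1 repeats the claim: "Recruitment of 380 women is required to achieve" at least 90% power for a difference of 0.05 g/cm². Section 13.3 fixes the primary analysis as a mixed model of the 1- and 2-year scans, "adjusted for the baseline BMD in the lumbar spine and the minimisation variables as fixed effects", apart from site, which is a random effect. The treatment contrast at 2 years is the primary comparison.

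**The concern.** Difference, SD, power and significance level are unchanged between the two calculations. The whole reduction from 382 to 304 therefore comes from the repeated-measures adjustment and the value of ρ put into it. Two things look wrong.

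First, the adjustment behaves like the one for an average over follow-up visits with no baseline covariate. The primary comparison is a single time point with a baseline covariate, and ρ acts on its required size in the opposite direction.

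Second, where the size rises with ρ, the cautious choice is a high value. The value taken is the top of a generic range with no bone-density source, while the same section holds bone-density figures that point well above it.

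At stake is whether the 90% and 80% figures describe this trial. They are the only statement in the protocol of what 380 or a smaller number of women would deliver, and recruitment was rated Red at the first feasibility review (section 13.3.2).

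**Working it through.** **Inputs.** Difference 0.05 g/cm², SD 0.15, two-sided 5%, 1:1 allocation, ρ = 0.6, 20% loss (all section 13.1.1); baseline-adjusted 2-year contrast (section 13.3).

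**1. Reproduce the printed sizes.** Per group, n = 2(z₀.₉₇₅ + z_power)² × SD² / difference².
- 90% power: 2 × (1.960 + 1.282)² × 9 = 189.1. The exact t-test gives 191, so 382 in total, as printed.
- Times (1 + 0.6)/2 = 0.8: 151.3, so 152 per group and 304 in total; 304/0.8 = 380, as printed.
- 80% power: 141.3 × 0.8 = 113.0, so 114 per group and 228 in total; 228/0.8 = 285, against 286 printed.

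The protocol prints no formula. A change-score factor, 2(1 − ρ), also equals 0.8 at ρ = 0.6, but it falls as ρ rises. Only (1 + ρ)/2 fits the statements that the size rises with ρ and reaches the t-test size at ρ = 1.

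**2. What that factor describes.** With two equally correlated measures, (1 + ρ)/2 is the variance of their mean relative to one measure. It contains no baseline term and does not target year 2. For a 2-year contrast without baseline adjustment and with complete data, the year-1 scan adds nothing: the factor is 1, and power with 304 is about 83% at any ρ. With baseline adjustment and correlation ρ with baseline, the factor is 1 − ρ².

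**3. What the protocol's figures suggest for ρ.** Read 0.05 as the usual smallest detectable difference, 1.96 × √2 × measurement SD.
- Measurement SD = 0.05/(1.96 × √2) = 0.018.
- Ceiling on ρ from measurement error alone = 1 − (0.018/0.15)² = 0.986.
- Adding a true between-scan change with SD τ (not in the documents), ρ = 1 − (2 × 0.018² + τ²)/(2 × 0.15²). For τ = 0.02, 0.03, 0.05 and 0.08 this gives 0.98, 0.97, 0.93 and 0.84.
- Conversely, ρ = 0.6 needs a within-woman change SD of 0.15 × √(2 × 0.4) = 0.134. If changes are normal around zero, about 71% of women would move by more than 0.05 g/cm² between the 1- and 2-year scans.

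**4. Power for 0.05 g/cm² (noncentral t).**

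| ρ | Factor (1+ρ)/2, 304 | Factor (1+ρ)/2, 228 | Factor 1−ρ², 304 | Factor 1−ρ², 228 |
|---|---|---|---|---|
| 0.6 | 90% | 80% | 95% | 88% |
| 0.8 | 86% | 75% | 99.8% | 99% |
| 0.9 | 84% | 73% | >99.9% | >99.9% |
| 0.98 | 83% | 71% | >99.9% | >99.9% |

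At ρ = 0.4, the bottom of the generic range, the planned contrast has just under 89% with 304; at 0.5 it has about 92%.

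**5. Difference detectable with 90% power, planned contrast.** (1.960 + 1.282) × 0.15 × √(2(1 − ρ²)/n), with n = 152 or 114 per group.
- 304 analysed: 0.045, 0.033 and 0.024 g/cm² at ρ = 0.6, 0.8 and 0.9.
- 228 analysed: 0.052, 0.039 and 0.028 g/cm².

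**The case against.** The arithmetic is right: every printed size follows from the stated inputs. The assumption is openly declared, the lack of accrued data is admitted, and within the quoted range the end giving the larger size was taken. In that limited sense the word *conservative* is coherent. All of this stands, but the range itself is generic.

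The case that ρ is higher is an inference. The documents give no measurement SD, and the smallest-detectable-difference convention is not printed. Measurement error bounds ρ only from above. Treatment switching (section 7.3), interruption for pregnancy (section 7.1.4) and the use of one scanner only where possible (section 8.3) all add within-woman variation. So the precision figure does not strictly contradict 0.6. It makes 0.6 hard to credit, because with SD 0.15 it would need a true yearly change SD of √(0.4 × 2 × 0.15² − 2 × 0.018²) = 0.132 g/cm².

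The strongest objection concerns direction. For the analysis actually planned, a low ρ is the cautious choice, and at 0.6 or above the claim of at least 90% power in section 3.1 is met. This stands, and it rules out reading the 83 to 86% figures as the power of this trial.

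Power is also not among the month-36 stop-go criteria, and section 13.1.1 attaches no decision to the 286 figure. This limits the practical consequence.

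**Conclusion.** The point holds as a fault in the justification. The printed sizes answer a different question from the primary comparison, and the value of ρ is not conservative in the calculation where it was used. At a bone-density-plausible ρ the 90% and 80% labels are wrong under either reading. They are too high by about 4 to 7 and 5 to 9 percentage points in the calculation used (ρ 0.8 to 0.98), and too low for the planned contrast, where power exceeds 99% with 304 and is about 99% or more with 228.

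A reader might infer that the trial is underpowered, or that the target should return to the 450 to 470 recruited that the printed approach would need at ρ of 0.9 to 0.98. The documents do not support that. Those numbers belong to an unadjusted average over visits, and the planned baseline-adjusted contrast has about 95% power with 304 even at ρ = 0.6.

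The conclusion rests on four assumptions: that (1 + ρ)/2 was the factor used, which the reproduced figures and the described behaviour support; that 0.05 is a conventional smallest detectable difference; that ρ lies between 0.8 and 0.98; and that the same ρ holds between baseline and 2 years. If the correlation with baseline were only 0.4, power with 304 would be just under 90%.

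**What to change.** In section 13.1.1, delete the description of 0.6 as conservative. Name the quantity being powered as the baseline-adjusted 2-year contrast, and give the variance factor used. Restate, there and in section 3.1, the power with 380 and with 286 recruited and the difference detectable with 90% power, over a stated bone-density-based range of ρ (for example 0.6, 0.8 and 0.9).

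Where enough scans have accrued, inform the range with estimates of the baseline-to-follow-up correlation and the SD, pooled over arms without allocation. The documents do not show how many paired scans exist, so the restatement should not wait for them. Keep the target of 380.

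The cost is a short calculation and a wording change in two sections. It needs no extra participants or scans, and type I error is unaffected because allocation is not used and the target stays fixed. The one drawback is that the printed justification for 304 and 286 has to be replaced.
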